5.2.2 Primary Estimand

Population: The population of interest are hospitalized patients between ≥ 18 and < 85 years old with confirmed critical COVID-19 disease.

Endpoint: Time to sustained clinical improvement.

Interventions: Received Sirukumab 5 mg/kg (IV single dose infusion on Day 1) and placebo (IV infusion on Day 1), both on top of SOC.

Intercurrent Events:

- Death as intercurrent event is handled in a composite strategy as it is the worst category on the clinical scale.
- The intercurrent event of the use of prohibited medication is handled in a treatment policy strategy: data will be used as observed.

- The intercurrent event of discharge to the alternate care settings ‘different hospital’, ‘acute care facility’, ‘subacute care facility’ or ‘hospice/palliative discharge’ is handled in a while on treatment strategy: see section 5.2.1
- The intercurrent event of discharge ‘against medical advice’ is handled in a hypothetical strategy: see section 5.2.1

Population-level summary measure:

Hazard ratio of ‘Sustained clinical improvement’ for experimental treatment versus placebo, from baseline until day 28.

5.2.3 Analysis Methods

All participants for which the trial is still ongoing at Day 28 and without sustained clinical improvement by Day 28 will be censored on Day 28. Participants that discontinue the study before day 28 will be censored at the last assessment of the CRS, unless they had an event of sustained clinical improvement prior to discontinuation. Participants that died at day 28 or earlier will be censored at day 28, irrespective of whether a clinical improvement occurred prior to death.

The primary hypothesis of this study is that Sirukumab in combination with SOC results in a statistically significant shorter time to sustained improvement (defined as an improvement of at least 2 categories relative to baseline on the 6-point ordinal CRS) versus placebo in combination with SOC, in participants with confirmed critical COVID-19.

The primary hypothesis will be evaluated based on the Logrank test, stratified for the stratification factors (age [<65 and ≥ 65 years] and use of IMV [yes/no]). This test will be performed 2-sided at a 5% significance level. The actual values of the stratification factors will be used, not as randomized.

The hazard ratio of sustained clinical improvement for experimental treatment versus placebo, from baseline until day 28 will be considered as the population-level summary measure of the treatment effect for the primary estimand. The hazard ratio will be estimated in a Cox proportional hazards model stratified for the stratification factors and with treatment as a single covariate. A value larger than 1 indicates the chance of improvement is larger in the experimental treatment group. The 95% Wald confidence interval will be added.

The Log-rank test might generate a different p-value compared to that of the Wald test of the hazard ratio. The Logrank test will be used for formal inference (and not the Wald p-value or CI from the hazard ratio).

Cumulative proportion of patients with clinical improvement, by treatment, will be provided using the complement of the Kaplan Meier curve. The analyses will be completed with the median time to clinical improvement (if reached) and the proportion of participants who had their clinical improvement on day 7, 14, 21 and 28; all per Kaplan Meier method. The complementary log-log transform method is used to calculate the 95% confidence intervals.

As a sensitivity analysis, a Cox proportional hazards model will be estimated that is stratified for the stratification factors, but also adjusted for additional baseline covariates on top of treatment. The covariates are the following: CRS at baseline (≤ 3 vs > 3), Remdesivir at baseline (yes/no), Glucocorticoids at baseline (yes/no), Number of Comorbidities (0/1/2/ ≥ 3), Sex (Male/Female), Race (Asian/Black or African American/White/Unknown or Not reported), Ethnicity (Hispanic or Latino/Not Hispanic or Latino), Free IL-6 at screening, CRP at screening, ferritin at screening, LDH at screening (high/low/normal) and albumin (low/not low) at screening. Each of the additional baseline covariates will be added to the model to estimate the individual effect of these covariates, after which a stepwise selection method will be applied. A covariate will be added to the model if it is significant at the 25% significance level, while the covariate in the model has to be significant at the 0.15% level for it to remain in the model. The hazard ratio will be estimated in the final Cox proportional hazard model.

Comorbidities considered: Obesity (BMI ≥ 30), Diabetes, Serious Heart Condition/Coronary Heart Disease, Chronic Obstructive Lung Disease, Chronic Kidney Disease and cancer. Time to sustained clinical improvement can be considered as a composite of two endpoints: time to improvement in the survivors as well as death by day 28. These two components will therefore also be analyzed separately. That is, the analyses described in the previous paragraph will be repeated in the subgroup of participants that do not die by day 28 and the analyses for the endpoint of death by day 28 are described in section [5.3](#).

At this moment it is difficult to predict whether prohibited medication will be used, in what frequency in the two treatment arms and what their efficacy might be. Therefore, the impact of prohibited medication will be explored retrospectively.

Analyses of qualitative comparison between pre-interim analysis and post-interim analysis for treatment effect on the primary endpoint in the population with confirmed critical COVID-19 disease will be conducted to check the consistency in the study.

The primary analysis will be repeated for the ITT population, including the participants with severe confirmed COVID-19 disease.

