2.6 Definition of Subgroups

Subgroups used for analyses of different endpoints are defined in the Table 2 below.

Descriptive statistics will be produced for the different subgroups.

Table 2: Subgroup definition

| Subgroup | Definition | Endpoints |
|------------------------------------|--|--|
| Age group (years) | 
 • <65 years • ≥ 65 years | 
 - Participants' demographics information, baseline disease characteristics, and disposition information - Selected Efficacy - Safety (selected laboratory test results and AE tables) |
| CRS score at baseline ¹ | 
 CRS ≤ 3 CRS ≤ 4 CRS=4 CRS=5 | 
 - Participants' demographics information, baseline disease characteristics, and disposition information - Selected Efficacy - Safety (selected laboratory test results and Adverse events results) |
| | | ○ |

| Subgroup | Definition | Endpoints |
|------------------------|--|--|
| Center ² | 
 Highest recruiter center (located over 2 sites) All other centers | Efficacy (primary and key secondary endpoints) |
| Interim Analysis | 
 Included in Interim Analysis Not included in Interim Analysis | Efficacy (primary and key secondary endpoints) |
| Free IL-6 at screening | 
 $\leq 33\%$ percentile > 33 and $\leq 66\%$ percentile $> 66\%$ percentile | Efficacy (primary and key secondary endpoints) |
| CRP at screening | 
 $\leq 33\%$ percentile > 33 and $\leq 66\%$ percentile $> 66\%$ percentile | Efficacy (primary and key secondary endpoints) |

¹ CRS=5 corresponds to “Use of IMV at the time of randomization”. For descriptive statistics, CRS score at baseline with the subgroups as defined will be used. For inferential statistics, the models should include a baseline CRS flag (≤ 3 /> 3) in combination with the stratification factor. Baseline CRS will not be included in the model.

² Highest recruiter center (located over 2 sites: US1006 & US10033)

Additional subgroup analysis may be specified in a separate analysis plan and reported separately from the clinical study report. These may include subgroups according to baseline C-Reactive Protein or baseline Albumin values.

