5.1.2 Stratification Factors

The actual values of the stratification factors will be used for all analyses.

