5.3.3 Analysis Method

The data will be analyzed according to the randomized treatment.

For the key secondary endpoints, the CMH analysis for difference in proportions, adjusted for the stratification factors (age [<65 and ≥ 65 years] and use of IMV [yes/no]) will be performed. The comparison between treatment groups will be based on CI-estimates and p-values obtained from this analysis.

A positive value on the common proportion (risk) difference using the Mantel-Haenszel method indicates that the proportion of participants with ‘Sustained clinical improvement at day 28’/‘death by day 28’ is larger in the experimental treatment group. The actual values of the stratification factors will be used, not as randomized.

As a sensitivity analysis, a logistic regression model will be estimated that is adjusted for the treatment group, but also adjusted for additional baseline covariates. The covariates are the following: CRS at baseline (≤ 3 vs > 3), Remdesivir at baseline (yes/no), Glucocorticoids at baseline (yes/no), Number of Comorbidities (0/1/2/ ≥ 3), Sex (Male/Female), Race (Asian/Black or African American/White/Unknown or Not reported), Ethnicity (Hispanic or Latino/Not Hispanic or Latino), Free IL-6 at screening, CRP at screening, ferritin at screening, LDH at screening (high/low/normal) and albumin (low/not low) at screening. Each of the additional baseline covariates will be added to the model to estimate the individual effect of these covariates, after which a stepwise selection method will be applied. A covariate will be added to the model if it is significant at the 25% significance level, while the covariate in the model has to be significant at the 0.15% level for it to remain in the model. In the final logistic regression model the treatment difference in proportions will be estimated. This will be done as follows: in each treatment group the proportion of participants with improvement will be estimated using the average value observed the study (across treatment groups) for both the continues and categorical covariates (based on 0/1 coding for categorical). The delta method will be used for the confidence interval.

Comorbidities considered: Obesity (BMI ≥ 30), Diabetes, Serious Heart Condition/Coronary Heart Disease, Chronic Obstructive Lung Disease, Chronic Kidney Disease and Cancer.

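### Covariates enter the SAP sensitivity models at 25% but stay only at 0.15%, with no reason given, so the adjusted estimate often contains none of the listed covariates

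*SAP*

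**What the plan says.** SAP 5.2.3 plans a sensitivity Cox model for the primary endpoint. It is stratified by age group and IMV and adjusted for covariates chosen from a list that includes remdesivir, glucocorticoids, number of comorbidities, demographics, free IL-6, CRP, ferritin, LDH and albumin. A first step fits covariates singly: "Each of the additional baseline covariates will be added to the model to estimate the individual effect of these covariates". Stepwise selection follows, with entry at the 25% level, "while the covariate in the model has to be significant at the 0.15% level for it to remain in the model". The treatment estimate is taken after selection: "The hazard ratio will be estimated in the final Cox proportional hazard model".

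SAP 5.3.3 repeats the list and both levels for the key secondary endpoints, where "a logistic regression model will be estimated that is adjusted for the treatment group, but also adjusted for additional baseline covariates". Again, "In the final logistic regression model the treatment difference in proportions will be estimated".

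The primary Cox model in 5.2.3 is "stratified for the stratification factors and with treatment as a single covariate".

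Two other places bear on whether age and IMV belong in the logistic model. Footnote 1 to Table 2 (SAP 2.6) asks inferential models to carry a baseline CRS flag "in combination with the stratification factor. Baseline CRS will not be included in the model". SAP 5.1.2 states: "The actual values of the stratification factors will be used for all analyses".

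The protocol leaves the sensitivity analyses to the SAP (Protocol 9.4.2), and neither document explains the 0.15% level.

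**The concern.** A stay level far stricter than the entry level makes the entry level almost irrelevant. The ratio is 25 / 0.15 ≈ 167, and in two-sided critical values the contrast is |z| > 1.150 to enter and |z| > 3.175 to stay. In a set of about 111 participants with 37 controls, few two-level covariates can reach the second threshold.

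The sensitivity analyses are there to show whether the treatment estimate survives adjustment for prognostic factors that may be unbalanced by chance. If selection removes every covariate, the final Cox model is the primary stratified Cox model under another name, and its agreement with the primary result is automatic. The final logistic model is then at most adjusted for age and IMV, as the CMH analysis already is.

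**Working it through.** **Inputs.** From SAP 1.4: 74 vs 37 participants; log-normal time to improvement in survivors with medians 16.8 and 28 days and SD 0.9 on the log scale; Day-28 mortality 20% vs 40%. From SAP 5.2.3 and 5.3.3: entry 25%, stay 0.15%. Covariate effects and prevalences are not in the documents. They are assumed, and shown over a range.

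**The plan's own figure.** Improvement by Day 28 is 0.6 × Φ(0) = 0.300 in control and 0.8 × Φ(ln(28/16.8)/0.9) = 0.8 × Φ(0.568) = 0.572 on sirukumab. Expected events are 74 × 0.572 + 37 × 0.300 = 53.4. Simulating the two-sided 5% log-rank test (20,000 runs) gives 81.6% power, so the stated figure of at least 80% is reproduced.

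**Cox model, one two-level covariate.** With prevalence q, the mean of the Wald statistic is μ = ln(HR) × √(53.4 q(1−q)), and P(stay) = Φ(μ − z). The critical value z is 3.175 at 0.15% and 1.440 at 15%. For HR 2 and q = 0.5, μ = 0.693 × √13.35 = 2.533, so P(stay) = Φ(−0.642) = 0.26.

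**Logistic model, one two-level covariate, N = 111.** Take p₀ and p₁ with OR 2 that average to the overall rate. Then SE² = 1/[111(1−q)p₀(1−p₀)] + 1/[111 q p₁(1−p₁)] and μ = ln 2 / SE. The overall rates are 53.4/111 = 0.481 for improvement and (74 × 0.20 + 37 × 0.40)/111 = 0.267 for death. For improvement at q = 0.5, p₀ = 0.396, p₁ = 0.567, SE = 0.386 and μ = 1.797, so P(stay) = Φ(−1.378) = 0.084.

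Probability of passing the stay test at HR or OR 2:

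| Prevalence | 50% | 30% | 20% | 10% |
|---|---|---|---|---|
| Cox, 0.15% | 0.26 | 0.20 | 0.13 | 0.05 |
| Cox, 15% | 0.86 | 0.81 | 0.72 | 0.53 |
| Improvement, 0.15% | 0.08 | 0.06 | 0.04 | 0.02 |
| Improvement, 15% | 0.64 | 0.58 | 0.50 | 0.35 |
| Death, 0.15% | 0.06 | 0.05 | 0.04 | 0.02 |
| Death, 15% | 0.55 | 0.54 | 0.48 | 0.35 |

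The failure rates at 0.15% are therefore 74–95% for HR 2 and 92–98% for OR 2. At 50% prevalence, an even chance of staying needs HR of about 2.4, or OR of about 3.4 (improvement) or 4.0 (death).

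**Continuous covariates.** For HR 2 per SD, μ = 0.693 × √53.4 = 5.07 and P(stay) = 0.97. For OR 2 per SD it is about 0.47–0.68, depending on the endpoint and assumed rates.

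**ITT set.** With about 211 participants and an assumed 48% with events (about 101), a two-level covariate with HR 2 stays with probability about 0.62, 0.51 and 0.35 at prevalence 50, 30 and 20%.

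**Whole procedure.** Stepwise selection was simulated in the Primary set with 11 usable candidates, three of them true two-level predictors at HR or OR 2. CRS ≤3 vs >3 is constant in this set and drops out. Selection was assumed to end when a covariate that has just entered is removed at once. No covariate was kept in 56–58% of trials for the Cox model, 87–94% for death and 81–87% for improvement. With age and IMV forced into the logistic model, the shares were 95% (death) and 86% (improvement). At a 15% stay level they were 0% for Cox and roughly 1–7% for the logistic endpoints. With all covariates null, a 15% stay level kept about 1.5–1.8 of them on average; 0.15% kept almost none.

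**The case against.** The strongest reply is that little depends on this. Treatment is randomised, the log-rank and CMH tests use no selection, and the SAP also plans single-covariate fits and free IL-6 and CRP tertile subgroups. Changing to 15% may also gain little for the key secondary endpoints. A comparison of the 5.3.3 estimator under the two stay levels (120 replicates per cell, three true predictors at OR 2) measured RMS distance from the model holding those predictors. It gave 0.030 at 15% and 0.032 at 0.15% for death, and 0.038 and 0.039 for improvement. For death the SD of the risk difference was larger at 15% (0.118 vs 0.105), and with all covariates null 15% did worse (0.029 vs 0.019).

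This stands as a limit on consequence and as a real cost of 15%. It does not supply a reason for 0.15%. A sensitivity model that usually selects nothing does not test what it is described as testing, and the single-covariate fits and subgroups are only partial substitutes.

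Four stronger readings are tempting and are not supported.

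- A reader might infer that any predictor with a ratio near 2 drops out. That holds for two-level covariates only. HR 2 per SD is a stronger effect than HR 2 between two equal groups, which corresponds to exp(0.5 × ln 2) = 1.41 per SD.
- A reader might infer that the treatment estimate would be materially wrong. The documents give no covariate effects from which to establish that.
- A reader might infer that the logistic model can end with treatment alone. The sentence in 5.3.3 does not name age or IMV, but the Table 2 footnote and 5.1.2 point towards including them.
- A reader might take 15% as certainly intended. A slip for 0.15 as a proportion is plausible, but nothing confirms it.

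**Conclusion.** The stay level is wrong as written, or at least unexplained, in both sections. In the Primary set it removes most two-level covariates of moderate strength, so the final-model HR or risk difference will often be unadjusted for the listed factors, and its agreement with the main analysis would then say little. The sizes rest on the SAP's design assumptions and on assumed covariate effects and prevalences. They treat covariates singly except in the stepwise simulation. Correlation among covariates and multi-level factors would mostly lower retention further. The effect is confined to supportive estimates, so this should be corrected but does not threaten the formal inference.

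A related mismatch is a separate point. SAP 5.4.2 analyses the other secondary incidence endpoints by this logistic model, while Protocol 9.4.4 assigns some of them to the key secondary technique, which is CMH. That would need reconciling at any stay level.

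**What to change.** Before database lock of the primary analysis:

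1. In SAP 5.2.3 and 5.3.3, state the intended stay level. If 0.15 was meant as a proportion, write 15% and accept the null covariates and the loss of precision shown above. If 0.15% was intended, give the reason.
2. In 5.3.3, add a sentence confirming that treatment, age group (<65, ≥65) and IMV (yes/no), at their actual values, are always in the logistic model and are not subject to selection. This agrees with the Table 2 footnote and 5.1.2.

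The cost is one number in two places and one sentence. Data collection, sample size and the formal tests do not change. Settling the level before lock also keeps the choice between 0.15% and 15% from being made once treatment results are known.

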5.3 Key Secondary Endpoints

5.3.1 Definitions

Similar as for the primary endpoint, the definitions as specified in section [5.2.1](#) will be used for the key secondary endpoints.

Clinical improvement at Day 28

Clinical Improvement is obtained if the score on the CRS improved with at least 2 categories at Day 28 with respect to the baseline score.

All-cause mortality up to Day 28

All-cause mortality is defined as score 6 on the CRS at Day 28.

5.3.2 Key Secondary Estimands

Clinical improvement at Day 28

Population: The population of interest are hospitalized patients between ≥ 18 and <85 years old with confirmed critical COVID-19 disease.

Endpoint: Sustained clinical improvement at Day 28 (yes/no)

Interventions: Received Sirukumab 5 mg/kg (IV single dose infusion on Day 1) and placebo (IV infusion on Day 1), both on top of SOC.

Intercurrent Events:

- Death as intercurrent event is handled in a composite strategy as it is the worst category on the clinical scale. Participants that died at Day 28 or earlier will be considered as failure (Sustained clinical improvement at Day 28=no), irrespective of whether a clinical improvement occurred prior to death.
- The intercurrent event of the use of prohibited medication is handled in a treatment policy strategy: data will be used as observed.
- The intercurrent event of discharge to the alternate care settings ‘different hospital’, ‘acute care facility’, ‘subacute care facility’ or ‘hospice/palliative discharge’ is handled in a while on treatment strategy: see section 5.2.1
- Participants that discontinue the study before Day 28 will be considered as failure (Sustained clinical improvement at Day 28=no), unless they had an event of sustained clinical improvement prior to discontinuation. In the latter scenario it will be considered a success (Sustained clinical improvement at day 28=yes).

Population-level summary measure:

The difference in proportion of participants with of ‘Sustained clinical improvement at Day 28’ for experimental treatment versus placebo.

All-cause mortality up to Day 28

Population: The population of interest are hospitalized patients between ≥ 18 and <85 years old with confirmed critical COVID-19 disease.

Endpoint: Death by Day 28 (Yes/No)

Treatment: Sirukumab 5 mg/kg (IV single dose infusion on Day 1) and placebo (IV infusion on Day 1), both on top of SOC.

Intercurrent events:

- The intercurrent event of the use of prohibited medication is handled in a treatment policy strategy: data will be used as observed.
- Participants that discontinue the study before Day 28 with a score > 1 on the CRS will be analyzed according to the composite strategy and will be considered as death on day 28 (Death by day 28=yes).

- Participants whose last score on the CRS was equal to 1 and that were not reported as having died before or at day 28 will be analyzed according to the composite strategy and they will be considered as alive (Death at Day 28=no).

Population level summary measure:

The difference in proportion of participants with ‘Death by day 28’ for experimental treatment versus placebo.

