1.3. Schedule of Activities (SoA)

Safety laboratory testing (hematology, chemistry, and coagulation tests) will routinely be performed by local laboratories (refer to Section 10.2 Appendix 2: Clinical Laboratory Tests and Section 10.3 Appendix 3: Clinical and Laboratory Assessments Described per Day).

	Screening Phase ^a	Phase Day 1 to Day 28			Post Day 28 Follow-up Phone Calls	
Day	Screening	Baseline ^a Day 1	Day 2 to Day 28 ^b or day of discharge from hospital ^{aa} , or study discontinuation, whichever comes first	Day 28 Visit if discharged earlier (Phone Call) Day 28 ±3 days	Day 56, Day 84, Day 112 ±7 days	
Week	Week 1	Week 1 (Day 2) to Week 4			Week 4	Week 8, 12, 16
General Screening/Baseline assessments						
ICF ^c	X					
Inclusion/exclusion criteria	X	X ^d				
Demographics, medical history ^c	X					
Targeted physical exam ^b	X		Any clinically significant findings to be reported			
Treatment administration						
Randomization ⁱ		X				
Administration of study intervention ⁱ		X				
Concomitant medication						
Concomitant medication recording	X	X	Throughout the study	X ⁿ	X ⁿ	
Respiratory function related assessments						
Type of supplemental oxygen	X	X	Once per day			
Resting SpO ₂ , FiO ₂ (if any) ^j	X	X	Minimum 4 times per day			
Arterial pH, PaO ₂ , PaCO ₂ ^j			As available			
Level of consciousness (Glasgow coma scale score) ^k	X	X	Once per day while in the ICU			
Pulmonary X-ray (or CT imaging or lung ultrasound if X-ray not available)	X ^{g,bb}		As per SOC, report upon worsening and last available			

	Screening Phase ^a	Phase Day 1 to Day 28				Post Day 28 Follow-up Phone Calls	
Day	Screening	Baseline ^a Day 1	Day 2 to Day 28 ^b or day of discharge from hospital ^{aa} , or study discontinuation, whichever comes first		Day 28 Visit if discharged earlier (Phone Call) Day 28 ±3 days	Day 56, Day 84, Day 112 ±7 days	
Week	Week 1		Week 1 (Day 2) to Week 4			Week 4	Week 8, 12, 16
General safety related assessments							
Standard 12-lead ECG	X ^{g,bb}		one ECG is to be taken between Day 4 and Day 8				
Vital signs (body temperature, pulse, SBP/DBP, respiratory rate)	X	X	As per SOC, minimum 4 times per day while in the ICU, afterwards once per day				
Any AE	X	X	Throughout the study				X ⁿ
Record discharge from ICU, discharge from hospital			As applicable				
Safety laboratory assessments^{dd}							
Hematology ^l	X ^g	X	Day 3, Day 7, Day 14, Day 21, Day 28 ^{cc}				
Chemistry ^l general safety	X ^g	X	Day 3, Day 7, Day 14, Day 21, Day 28 ^{cc}				

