 - General safety chemistry: total protein, albumin, aspartate aminotransferase (AST), alanine aminotransferase (ALT), alkaline phosphatase (ALP), total bilirubin, glucose, sodium, potassium, calcium, phosphate, magnesium, chloride, bicarbonate, creatinine, blood urea nitrogen (BUN), creatine phosphokinase (CPK), lactate dehydrogenase (LDH), lactate, and troponin. If ALT or AST >3x ULN or 3x the entry level (if entry levels were >ULN), also provide conjugated bilirubin (direct), unconjugated bilirubin (indirect).
- m. Culture results (bacterial, fungal, or viral) including site of infection and specimen source (bronchoalveolar lavage [BAL], tracheal aspirate, sputum, blood, urine, etc.), performed as part of patients' workup for new infections, should be reported. Analyses will be performed by the local laboratory.
- n. For participants discharged or who discontinued the study prior to Day 28 and did not withdraw consent, phone calls will be conducted on Day 28 and during the post Day 28 Follow-up Phase to record concomitant medication, the vital status, the occurrence of AEs, self-reported oxygen need, self-reported pregnancy status and the history of readmission since last contact.
- o. Whenever possible, vital status will be recorded if the patient is alive. If the participant is deceased, date and cause of mortality should be recorded in the eCRF. Death should be documented as SAE.
- p. NP swabs will be used to collect secretions from participants to explore quantification of viral load of SARS-CoV-2. For each participant, NP sampling should be done at approximately the same time (± 4 hours) on each sampling day and from the same nostril.
- q. If an NP sample for detection of SARS-CoV-2 (local SOC) will be collected on the same day as the NP sample for quantification of SARS-CoV-2 (central lab), only one NP sample should be collected. The sample should be aliquoted and the remaining aliquots of the NP samples should be stored and sent to the central lab for quantification of SARS-CoV-2.
- r. SARS-CoV-2 positivity should be documented based on local testing on any specimen, by RT-PCR, any time before randomization. This might require a local test using an NP swab obtained at screening.
- s. After randomization, SARS-CoV-2 positivity will be confirmed in a central lab by quantitative RT-PCR. The baseline sample needs to be collected predose, as close as possible to dosing.

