7.2. Participant Discontinuation/Withdrawal From the Study

A participant will be withdrawn from the study for any of the following reasons:

- Lost to follow-up
- Withdrawal of consent
- Death

When a participant withdraws before study completion, the reason for withdrawal is to be documented in the eCRF and in the source document.

Withdrawal of Consent

Participants who withdraw consent will be offered an optional Safety Follow-up Visit (call), that will occur the day of consent withdrawal and will consist of the same assessments as at the Day 28 (or day of discharge) visit.

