7.3. Lost to Follow-up

Lost to follow-up concerns the Phone Call Visits. A participant will be considered lost to follow-up if he or she is unable to be contacted by the study site. A participant cannot be deemed lost to follow-up until all reasonable efforts made by the study-site personnel to contact the participant are deemed futile. The following actions must be taken:

- Before a participant is deemed lost to follow up, the investigator or designee must make every reasonable effort to regain contact with the participant (where possible, 3 telephone calls, e-mails, fax, and, if necessary, a certified letter to the participant's last known mailing address, or local equivalent methods). These contact attempts should be documented in the participant's medical records.
- Should participants continue to be unreachable, they will be considered to have withdrawn from the study and documented as 'lost to follow-up' in the eCRF.
- Site personnel, or an independent third party, will attempt to collect the vital status of the participant within legal and ethical boundaries for all participants randomized, including those who did not get study intervention. Public sources may be searched for vital status information. If vital status is determined as deceased, this will be documented and the participant will not be considered lost to follow-up. If the participant withdrew consent, the vital status information available after consent withdrawal will not be collected in the eCRF and the participant will be considered to have discontinued from the study for consent withdrawal. Sponsor personnel will not be involved in any attempts to collect vital status information.

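### SAP 5.3.2 counts a participant who discontinues before Day 28 with a CRS above 1 as dead even when recorded alive at Day 28, and no designated sensitivity analysis of the mortality test counts recorded deaths only

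*SAP*

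**What the plan says.** SAP 5.3.1 defines all-cause mortality as a CRS score of 6 at Day 28. SAP 5.2.1 sets the CRS to missing after discontinuation for any reason other than death. SAP 5.3.2 fills that gap with two rules:

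- Discontinued before Day 28 with a score above 1: "will be analyzed according to the composite strategy and will be considered as death on day 28 (Death by day 28=yes"). Vital status is not mentioned.
- "Participants whose last score on the CRS was equal to 1 and that were not reported as having died before or at day 28": counted as alive. This rule does use reported death.

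The protocol plans to collect the missing information. Footnote n of the Schedule of Activities states: "For participants discharged or who discontinued the study prior to Day 28 and did not withdraw consent, phone calls will be conducted on Day 28". Vital status is one of the items recorded. Under Protocol 7.3, site staff or a third party "will attempt to collect the vital status of the participant within legal and ethical boundaries for all participants randomized", and public sources may be searched. There is one limit: "If the participant withdrew consent, the vital status information available after consent withdrawal will not be collected in the eCRF".

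The formal test is a CMH analysis of the difference in proportions, adjusted for age group and invasive ventilation (SAP 5.3.3). The single sensitivity analysis named there is a covariate-adjusted logistic regression on the same outcome.

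**The concern.** The endpoint is labelled death by Day 28, and for a participant recorded as alive on that day the first rule assigns the wrong value. Two neighbouring bullets treat vital status differently, and no reason is given.

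Mortality is the third test in the hierarchy (Protocol 9.4), so the error would sit in a formally tested result. The planned CMH output does not separate recorded from imputed deaths. Imputed deaths that occur equally in both arms mainly dilute the effect. If they differ by arm, they bias the comparison. Protocol 2.1.1 reports that an Advisory Committee could not definitely attribute a mortality imbalance in the rheumatoid arthritis programme to chance or study design. A mortality result for this drug should therefore be traceable to actual deaths.

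**Working it through.** **Step 1. Can the rule meet a recorded survivor?** Protocol 7.2 states "A participant will be withdrawn from the study for any of the following reasons" and lists loss to follow-up, consent withdrawal and death.

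- Death gives score 6, so there is no conflict.
- After consent withdrawal no status is collected, so there is no conflict.
- Loss to follow-up remains. SAP 5.2.1 (hospitalization rule 1) keeps the CRS above 1 after discharge to another hospital, an acute or subacute facility, or hospice. The contact is the "Day 28 Visit if discharged earlier (Phone Call) Day 28 ±3 days", so it can fall from Day 25 (28 − 3). A participant can be recorded as lost before Day 28 and later be found alive. For deaths, Protocol 7.3 says: "If vital status is determined as deceased, this will be documented and the participant will not be considered lost to follow-up". It has no matching sentence for someone found alive, who therefore stays a discontinuer and is counted dead.

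The route is narrow, but the documents allow it.

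**Step 2. The plan's own figure.** SAP 1.4 gives 40% vs 15% mortality, 37 control and 74 sirukumab, one-sided 5%, and power of at least 80%. The normal approximation gives 88.7%. Exact enumeration of the unstratified pooled test gives 89.8%. The stated power is correct.

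**Step 3. One recorded survivor counted as dead.** With c control and t sirukumab deaths and p̄ = (c + t)/111:

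z = (c/37 − t/74) / √[p̄(1 − p̄)(1/37 + 1/74)], rejecting if z > 1.645.

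Example with c = 15, t = 18: p̄ = 33/111 = 0.297, difference 0.405 − 0.243 = 0.162, standard error 0.092, z = 1.762, p = 0.039.

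| Recorded deaths (control vs sirukumab) | p | After one survivor is counted dead | p |
|---|---|---|---|
| 15/37 vs 11/74 | 0.0013 | 15/37 vs 12/74 | 0.0024 |
| 15/37 vs 18/74 | 0.039 | 15/37 vs 19/74 | 0.055 |
| 13/37 vs 16/74 | 0.063 | 14/37 vs 16/74 | 0.035 |

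**Step 4. How often one case changes the result.** Fix one recorded survivor in one arm, draw deaths among the others as Binomial(n − 1, p), and analyse the same data with that participant alive and then dead.

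| True mortality (control vs sirukumab) | Arm of the case | Reject, counted alive | Reject, counted dead | Result differs |
|---|---|---|---|---|
| 40% vs 15% | sirukumab | 90.2% | 86.9% | 3.3% |
| 40% vs 15% | control | 87.8% | 92.7% | 4.9% |
| 40% vs 40% | sirukumab | 5.6% | 4.1% | 1.5% |
| 40% vs 40% | control | 3.9% | 6.7% | 2.8% |

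The single-stratum CMH statistic gives nearly the same shares: 3.5%, 4.9%, 1.5% and 2.8%.

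**Step 5. Illustration for all imputed deaths, including unknown status.** Let a share d of survivors be counted dead. The analysed rate is then p + (1 − p)d. The documents give no discontinuation rate, so d is an assumption.

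- Same d in both arms, 40% vs 15%: power 89.8% (d = 0), 84.3% (d = 5%, rates 43.0% vs 19.25%), 78.2% (d = 10%, rates 46.0% vs 23.5%).
- Equal true mortality, 5% in control only: rejection in favour of sirukumab 8.9% at 40% mortality (5.0% with no imputation) and 11.0% at 30% (5.4% with none).
- Equal true mortality of 40%, 5% in sirukumab only: 2.5%.
- If a quarter of the affected control survivors had recorded status (assumption), using it would bring 8.9% down to 7.8%; if half, to 6.8%.

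**The case against.** Five points can be made for the plan.

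1. **Few or no participants qualify.** Loss to follow-up concerns the phone visits and cannot be declared until all reasonable contact efforts have failed. A participant who answers the Day 28 call is not lost. This stands, and it limits the size of the problem.
2. **The composite strategy is declared.** Counting discontinuation as failure matches the handling of the first key secondary endpoint. This is a fair defence where status is unknown, and that use is not disputed. It does not justify labelling a recorded survivor as dead in an endpoint called all-cause mortality.
3. **Recorded deaths appear elsewhere.** Protocol 9.4.4 compares category 6 mortality by the same techniques. The proportion alive at Day 28 is an endpoint. Further sources are the daily CRS tables, the Day 28 proportional odds model and the tables of adverse events leading to death. All true, but none is designated as a sensitivity analysis of the CMH mortality test, and SAP 5.4 does not carry the category 6 comparison as a separate analysis.
4. **Step 5 covers more than the defect.** Correct. It includes imputations that are accepted here, and the one-sided imbalance is an assumption in a double-blind, single-infusion trial.
5. **The step 5 error rates ignore the hierarchy.** Also correct. Mortality is tested only after the primary and first key secondary endpoints succeed. A simulation of the hierarchy (8,000 runs, unstratified, 40% mortality in both arms, 5% of control survivors counted dead, random discontinuation days assumed) gave about 1.2% mortality rejection with no effect on improvement. With the planned improvement effect in survivors it gave about 6.5%, against about 4% if only true deaths count.

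**Conclusion.** The concern holds. As written, SAP 5.3.2 can override a recorded survival in a formally tested mortality endpoint, and no designated sensitivity analysis would show it.

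The size attributable to this defect is that of steps 3 and 4: 1.4 or 2.7 percentage points per case, and a 1.5% to 4.9% chance that one case changes the test result, given that such a case exists. At the planned death rates one case leaves the conclusion intact. These figures rest on 74 vs 37 participants and an unstratified test. Step 5 describes the whole imputation under assumed rates and outside the hierarchy. It shows why recorded and imputed deaths should be separable and does not measure the recorded-alive error. The stated power is correct. The point should be fixed because the value is wrong where the case arises and the remedy is small.

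**What to change.** - **SAP 5.3.2.** Replace the rule for scores above 1 with: *Recorded vital status at Day 28, from any source where consent allows its collection, determines Death by Day 28. Only if Day 28 vital status is unknown is a participant who discontinued before Day 28 with a score >1 on the CRS counted as Death by Day 28 = yes.*
- **SAP 5.3.1.** Add to the mortality definition: *or imputed as in 5.3.2.*
- **SAP 5.3.3.** Add: *As a sensitivity analysis, the CMH analysis is repeated counting recorded deaths only; recorded and imputed deaths are tabulated by arm.*

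The override corrects only participants recorded as alive. Imputed deaths of unknown status stay in the main test, and the added sensitivity analysis shows their influence. The cost is a few sentences, one further CMH run and one table, using vital-status data the protocol already plans to collect. After consent withdrawal those data are not available, and the imputation continues to apply.
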